---------------------------	---

Test Product, Dose, and Mode of Administration	
The andexanet IV bolus will be initiated within 30 minutes prior to the start of surgery (i.e., the first incision) and must be completed prior to surgery start. The bolus will be followed by a continuous infusion lasting at least 120 minutes, irrespective of the length of the surgery. The continuous infusion must be ongoing at the start of surgery, and must continue until the end of surgery even if extended treatment is required. There are 2 possible dosing regimens as described below:
			
Andexanet Dose	Timing of Last Dose of FXa Inhibitor	Initial Dose		Extended Infusion
		Initial IV Bolus	Initial Follow-on IV Infusion	
Low Dose	
≥ 8 hours OR < 8 hours for
 
 • Rivaroxaban 10 mg • Apixaban 2.5-5 mg • Enoxaparin 40 mg • Edoxaban 30 mg 	400 mg at a target rate of 30 mg/min	4 mg/min for at least 120 minutes irrespective of the duration of surgery	Extended infusion (beyond 120 minutes) may be administered at 4 mg/min (low-dose) for up to 4 additional hours *
High Dose	
< 8 hours
 
 • Rivaroxaban > 10 mg; • Apixaban > 5 mg • Enoxaparin > 40 mg • Edoxaban 60 mg 
OR
 
> 15 hours or unknown time
 
 • Local anti-fXa > 100 ng/mL (0.5 IU/mL for enoxaparin) 	800 mg at a target rate of 30 mg/min	8 mg/min for at least 120 minutes irrespective of the duration of surgery	

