Inclusion Criteria	
All of the following criteria must be met for the patient to be eligible:
 
 1. Either the patient or their medical proxy (or legal designee) has given written informed consent. 2. Age \geq 18 and $<$ 85 years old. 3. Requires urgent surgical intervention that must occur within 12 hours of consent, for which reversal of anti-fXa activity is judged necessary. 4. Treatment with an oral FXa inhibitor (apixaban [last dose 2.5 mg or greater], rivaroxaban [last dose 10 mg or greater], edoxaban [last dose 30 mg or greater] or enoxaparin [\geq 1 mg/kg/d]): 5. \leq 15 hours prior to start of surgery. 6. $>$ 15 hours prior to start of surgery or unknown time from the last dose, if documented anti fXa activity is $>$ 100 ng/mL ($>$ 0.5 IU/mL for enoxaparin, or over the equivalent IU/mL threshold on a low molecular weight heparin assay; see Laboratory Manual) within 2 hours prior to consent. Note: Patients enrolled in this manner should receive a high-andexanet dosing regimen. 7. Have a negative pregnancy test documented prior to enrollment (for women of childbearing potential). 8. Willingness to use highly effective methods of contraception through 30 days following study drug dose (for female and male patients who are fertile).

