Exclusion Criteria	
If a patient meets any of the following criteria, he or she is not eligible:
 
 1. Surgery for which the risk of clinically meaningful uncontrolled or unmanageable bleeding is low. 2. Acute life-threatening bleeding (ISTH criteria) at the time of Screening: 
 a. The patient has acute-overt bleeding that is potentially life-threatening, e.g., with signs or symptoms of hemodynamic compromise, such as severe hypotension, poor skin perfusion, mental confusion, low urine output that cannot be otherwise explained. b. The patient has overt bleeding associated with a fall in hemoglobin level by $\geq 2\text{g/dL}$, OR, a hemoglobin $\leq 8\text{ g/dL}$ if no baseline hemoglobin is available. c. The patient has acute bleeding in a critical area or organ, such as pericardial, intracranial, or intraspinal. 3. Any surgical procedure that involves the intraoperative use of systemic, intravascular, unfractionated heparin. 4. Primary procedure for efficacy assessment is a non-surgical interventional procedure (e.g, lumbar puncture, skin biopsy, cardiac catheterization, endoscopic retrograde cholangio-pancreatography). 5. Expected survival of < 1 month due to comorbidity. 6. Known “Do Not Resuscitate” order or similar advanced directive. 7. The patient has a recent history (within 30 days prior to screening) of a diagnosed TE as follows: venous thromboembolism (including deep vein thrombosis, pulmonary embolism, intracardiac thrombus), myocardial infarction (including asymptomatic troponin elevations), disseminated intravascular coagulation, acute traumatic coagulopathy, cerebrovascular accident, transient ischemic attack, unstable angina pectoris hospitalization, or severe peripheral vascular disease. 8. Acute decompensated heart failure or cardiogenic shock at the time of screening. 9. The patient has sepsis or septic or severe hemorrhagic shock at the time of Screening. 10. The patient has heparin-induced thrombocytopenia (with or without thrombosis). 11. Inherited coagulopathy (e.g., anti-phospholipid antibody syndrome, protein C/S deficiency, Factor V Leiden) at time of Screening. 12. Platelet count $< 80,000/\mu\text{L}$ at the time of Screening. 13. Last dose of apixaban $< 2.5\text{ mg}$, rivaroxaban $< 10\text{ mg}$, edoxaban $< 30\text{ mg}$, or enoxaparin 40 mg. 14. The patient is pregnant or a lactating female. 15. The patient has received any of the following drugs or blood products within 7 days of enrollment: 
 o Vitamin K antagonists (e.g., warfarin). o Dabigatran. o Prothrombin complex concentrate products (e.g., Kcentra[®]) or recombinant factor VIIa (e.g., NovoSeven[®]). o Whole blood, plasma fractions. 
Note: Administration of tranexamic acid, platelets or packed red blood cells is not an exclusion criterion.
 16. The patient was treated with an investigational drug < 30 days prior to Screening. 17. Prior treatment with andexanet. 18. Known hypersensitivity to any component of andexanet. 19. Known allergic reaction to hamster proteins. 20. Known or suspected (i.e., presumed positive) COVID-19-related illness at the time of Screening.

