3.0 INVESTIGATIONAL PLAN

3.1. Overall Study Design and Plan: Description

This is a Phase 2 multicenter, prospective, open-label, proof-of-concept study of andexanet alfa (referred to subsequently as “andexanet”) to determine the efficacy and safety of andexanet in patients who require urgent surgery (must occur within 12 hours of consent) who have, within 15 hours prior to surgery, received 1 of the following FXa inhibitors: apixaban, rivaroxaban, edoxaban, or enoxaparin. The start of surgery must be within 15 hours following the last dose of FXa inhibitor. If the time from last dose of FXa inhibitor is unknown or greater than 15 hours, patients with a local anti-fXa activity level obtained within 2 hours prior to consent > 100 ng/mL (> 0.5 IU/mL for patients taking enoxaparin) may be enrolled. Patients enrolled in this manner should receive a high-andexanet dosing regimen. In such cases, the start of surgery must begin no greater than 4 hours after the blood collection for the local test. The prespecified time periods and/or anti-fXa activity levels are designed to ensure patients have sufficiently high anti-fXa activity levels.

Patients will receive 1 of 2 dosing regimens of andexanet based on which FXa inhibitor they received and the dose and timing of the most recent dose of FXa inhibitor. Patients will receive an IV bolus of andexanet administered over approximately 15 to 30 minutes (depending on dose), followed immediately by an IV continuous infusion of andexanet for 2 hours, irrespective of the duration of surgery. The bolus must be completed immediately prior to the start of surgery (i.e., at the first incision; designated as Time 0). The infusion should continue from prior to the start of surgery (initial skin incision) until the end of surgery (close of skin incision, or, if skin closure is not completed by intention, an equivalent milestone such as dressing or packing the surgical incision). If the end of surgery occurs prior to completion of the initial 2-hour infusion, the infusion should continue into the postoperative period until it is completed (120 minutes). Additional andexanet, be it for extended treatment or re-dosing, may be given at the discretion of the Investigator when specific criteria regarding duration of surgery and/or postoperative complications are met (see Section 6.2).

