3.5. Safety Plan and Monitoring

The study will be conducted in patients who are hospitalized. As such, treatment with andexanet and subsequent monitoring will be done in a medical setting. It is expected that patients requiring urgent surgery will remain hospitalized for at least 12 hours, the timeframe for the primary efficacy evaluations. During the first 12-hour period (Study Day 1), AEs, vital signs, physical examinations, and laboratory testing will be performed as indicated in Appendix A to monitor safety. Enrolled patients will be closely monitored during the period where they are most vulnerable and the risk of thrombosis is highest.

Survival status will be ascertained on Study Day 30, and, if applicable, cause of death will be recorded. Antibody samples will be taken at baseline and Day 30 to assess immunogenicity against andexanet, FX, FXa, nAb, and HCPs. Due to the ongoing severe acute respiratory syndrome coronavirus 2 (SARS-CoV-2/COVID-19) pandemic, the Day 30 visit may be conducted by phone; considerations for laboratory samples are discussed in Section [3.7](#).

Of the 352 patients, 9.7% of patients with acute major bleeding in ANNEXA-4 experienced protocol-defined, adjudicated TEs that occurred within 30 days of andexanet treatment. While the attributability of these events to andexanet is uncertain, it is significantly possible that they will occur in the current study, given the anticipated enrolled population, for which reversal of anticoagulation may expose the underlying risk of TEs, and andexanet's known effects on coagulation biomarkers such as D-dimer, F1+2, and TFPI. In this study, patients with TEs within 30 days of Screening, those with a history of hypercoagulable states, and those who received procoagulant products within 7 days of Screening will not be eligible for the study due to their much greater risk for TEs in general and following anticoagulation reversal. In this study, TEs will be considered AEs of special interest (AESIs) and will be reported within 24 hours to the

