7.2.2. Blood Products

To maintain uniformity in transfusion practices across study participants, it is strongly suggested that the trigger for PRBC transfusion is hemoglobin ≤ 8.0 g/dL (± 1 g/dL). The hemoglobin triggering a transfusion, clinical stability factors (e.g., shock) influencing the decision to transfuse, as well as the number of units transfused should be recorded on the eCRFs.

Whole blood and platelet transfusions may be administered according to standard institutional/local practices and/or guidelines. Investigators may consider using pro-coagulant factor infusions (e.g., 3- or 4-factor PCC/activated PCC, rfVIIa, plasma, FFP) per their judgement in case of hemodynamic necessity. Otherwise, treatment with the above products is strongly discouraged, though not prohibited, during the entire 30-day observation period.

Use of procoagulant factor infusions (e.g., 3- or 4-factor PCC/activated PCC, rfVIIa, plasma, FFP) and whole blood intraoperatively will result in the patient being considered having poor hemostatic efficacy (see [Table 3](#)) with andexanet.

Use of blood products, including number of units transfused and the date and time of administration should be recorded on the eCRFs.

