10.1.8. Patient Identification Numbers

Patients will be considered to be in Screening once they have signed the ICF. At this time, patients will be assigned a patient identification number. Patients will be considered to have enrolled in the study once they have signed informed consent and met the inclusion and exclusion criteria.

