11.3.3. Efficacy Analysis Population

The efficacy analysis population will include all enrolled patients who receive any amount of andexanet treatment, undergo surgery, and have a baseline anti-fXa activity analyzed by central laboratory at or above the evaluability threshold (75 ng/mL for apixaban, edoxaban and rivaroxaban, and 0.25 IU/mL for enoxaparin). The primary, secondary, and exploratory efficacy endpoint will be analyzed based on the efficacy analysis population.

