11.5.1. Definitions

Hemostasis will be assessed from the start of surgery to the end of the procedure. Categories for the assessment of intraoperative hemostasis are provided in Table 3.

Table 3: Intraoperative Hemostasis Categories

Category	Definition
Excellent	Normal hemostasis during the procedure
Good	Mildly abnormal hemostasis as judged by quantity or quality of blood loss (e.g., slight oozing from surgical wounds)
Moderate	Moderate abnormality in intraprocedural hemostasis (e.g., controllable bleeding) but no need for additional systemic procoagulant products *
Poor	Severe hemostatic abnormality during the procedure (e.g., severe refractory hemorrhage) and need for additional systemic procoagulant products *

* Tranexamic acid excluded.

The evaluation period for anti-fXa activity covers the period of time from 5 minutes following the end of the andexanet bolus to just prior to the end of the andexanet infusion. The baseline measurement will be the last value obtained prior to andexanet treatment.

The hemostasis evaluation would exclude unexpected blood loss due to surgical complications that may cause uncontrolled bleeding, such as unintended injury of a major vessel or parenchymal tissue.

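### Procoagulant or blood products given after enrollment but before incision fall outside both the eligibility bar and the failure rule, so such patients can be counted as andexanet successes

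*Protocol*

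**What the plan says.** Exclusion criterion 15 (Protocol Synopsis and Section 4.2) applies where "The patient has received any of the following drugs or blood products within 7 days of enrollment". The list includes PCC, recombinant factor VIIa, whole blood and plasma fractions. Section 3.5 states a similar bar from a different anchor: "those who received procoagulant products within 7 days of Screening will not be eligible".

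Section 10.1.8 fixes the moment of enrollment: "Patients will be considered to have enrolled in the study once they have signed informed consent and met the inclusion and exclusion criteria". Inclusion criterion 3 sets the outer limit to incision: "Requires urgent surgical intervention that must occur within 12 hours of consent".

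Section 7.2.2 allows procoagulant factor infusions for hemodynamic necessity. Otherwise it discourages them, without banning them, throughout the 30-day observation period. Its failure rule for procoagulant factor infusions ends "and whole blood intraoperatively will result in the patient being considered having poor hemostatic efficacy". Section 11.5.1 sets the same window for the rating scale: "Hemostasis will be assessed from the start of surgery to the end of the procedure".

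Section 11.3.3 defines the analysis set: "The efficacy analysis population will include all enrolled patients who receive any amount of andexanet treatment, undergo surgery", plus a central-laboratory baseline anti-fXa activity at or above the threshold. It sets no condition on other procoagulants. Section 11.5.2.1 leaves non-evaluability to the EAC Charter.

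**The concern.** Two rules limit how far another procoagulant's effect can be credited to andexanet. One looks back from enrollment, and the other begins at incision. They do not meet. The same product makes a patient ineligible if given just before enrollment and a failure if given just after incision. Given in between, it has no stated consequence for the primary endpoint.

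The primary result is a single-arm proportion with a confidence interval (Sections 11.2 and 11.5.3), and Section 3.1 says the study will inform a randomized Phase 3 trial. Without a control arm, a co-intervention cannot cancel out in a comparison. The scenario is plausible on the protocol's own account. Section 3.4.2.2 describes PCC as de facto standard care for uncontrolled bleeding on these anticoagulants and cites case series of its use before urgent surgery.

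**Working it through.** **Status of one dose by timing**

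| When the product is given | Governing text | Consequence for the primary endpoint |
|---|---|---|
| In the 7 days before enrollment | Exclusion 15 | Not eligible |
| Enrollment to start of bolus | None stated | In the efficacy set; any rating possible |
| Start of bolus to incision | None stated | In the efficacy set; any rating possible |
| During surgery | Section 7.2.2 | Poor, hence ineffective |

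Section 10.1.7 has eligibility judged once screening is complete and states no re-check before dosing. The Screening anchor in Section 3.5 does not help: under Section 10.1.8 Screening starts at consent, no later than enrollment.

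**Length of the gap**

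- General limit: at most 12 h from consent (inclusion 3), less the time from consent to enrollment.
- Local-assay route (last dose more than 15 h ago or at an unknown time): "the start of surgery must begin no greater than 4 hours after the blood collection for the local test". That sample is taken 0 to 2 h before consent, so consent to incision is at most 4 − 2 = 2 h to 4 − 0 = 4 h.
- Appendix A: consent and eligibility fall between 2 h and 45 min before the start of surgery.
- The part after bolus start is at most 30 min (Section 6.2).

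**The plan's own precision figure**

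Section 11.6: 100 × (1 − 0.20) = 80 evaluable. The worst-case normal half-width is 1.96 × √(0.5 × 0.5 / 80) = 10.96%, which reproduces the stated figure of less than 11%.

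**Illustrative effect**

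The starting value is an assumption. The earlier study in bleeding patients reported 81.9% effective hemostasis (Section 1.4.7), and 0.819 × 80 = 65.5, taken as 66. So 66/80 = 82.5%. The number k of affected patients rated as successes is also assumed, because the protocol gives no frequency.

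- Removed from the set: (66 − k)/(80 − k). For k = 1, 65/79 = 82.3%; for k = 4, 62/76 = 81.6%. The shift is 0.2 to 0.9 points.
- Counted as failures: (66 − k)/80. For k = 1, 65/80 = 81.3%; for k = 4, 62/80 = 77.5%. The shift is 1.25 to 5 points.
- If one affected patient had instead been rated Moderate or Poor, removal would raise the estimate: 66/79 = 83.5%.

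**The case against.** The strongest reply is that the EAC may already deal with this. It must confirm the primary endpoint, it is blinded only to anti-fXa levels, and its Charter holds the non-evaluable criteria. Section 10.4.4 has products recorded with date, time and reason, including those given before surgery. This stands in part: the documents cannot show that such patients would be counted as successes, only that no rule in the protocol prevents it. The hemostasis form sent to the EAC (Administrative Change Letter 2) has no field for products given before incision.

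A second reply is that the case should be uncommon. Life-threatening bleeding and hemorrhagic shock are excluded at Screening, the products are discouraged outside hemodynamic necessity, and Section 3.4.2.2 says guidelines generally do not recommend preventive PCC. This stands, and it is why the number is probably small.

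A third is that exclusion 15 was written for thrombotic risk, the reason given in Section 3.5, and not for attribution. That is fair, but the failure rule in Section 7.2.2 does concern attribution, and it starts at incision whatever the motive for the exclusion.

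A reader might also take the exclusion's wording to reach forward from enrollment, since it does not say before. But an eligibility criterion is judged at enrollment, and a forward reading would clash with Section 7.2.2, which permits the products afterwards.

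Finally, sensitivity analyses are often left to the statistical analysis plan. That is true of the extra reporting proposed here. The failure window and the analysis set, however, are fixed in the protocol itself.

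**Conclusion.** The boundary gap is real: the stated rules let a patient who received another procoagulant after enrollment and before incision count as an andexanet success, subject to the unseen EAC Charter. It merits correction, but its likely size is modest. With one to four affected successes among 80, the estimate moves by 0.2 to 0.9 points if they are removed and by 1.25 to 5 points if they are counted as failures, against a stated margin just under 11 points. Both k and the 82.5% starting value are assumptions.

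Three stronger readings are not supported. A reader might infer that the gap can only inflate the result. Crediting andexanet is the likelier direction, but recipients may be worse bleeders who are rated Moderate or Poor, or who become poor through EAC-confirmed post-surgical bleeding (Section 7.3), so the net direction is not certain. A reader might take 5 points as the bias. That requires four affected patients, all rated as successes and all recoded as failures. And a reader might take 12 h as the typical exposure. It is a ceiling, and both the local-assay route and Appendix A imply much less.

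**What to change.** Change the analysis rules only; which products may be given is not touched.

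1. In Sections 7.2.2 and 11.5.2.1, start the poor-outcome rule for the exclusion-15 procoagulant and blood products at the start of the andexanet bolus instead of at incision. The exploratory red-cell transfusion endpoints in Section 11.5.2.3 already use that anchor.
2. In Section 11.3.3, treat use between enrollment and bolus start as pre-enrollment use is treated: out of the Efficacy Analysis Population, but kept in the safety population. Align this with the non-evaluable criteria in the EAC Charter.
3. Report the primary proportion with these patients as rated, without them, and with them counted as failures.

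The timing data are already collected under Section 10.4.4. The cost is a few sentences, additional table rows and a slightly smaller efficacy set, with a correspondingly slightly wider confidence interval. Separately, the enrollment and Screening anchors for the exclusion, and the differing consent-to-surgery limits, should be reconciled.

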*** Extended Infusion (Additional low-dose 4mg/min infusion up to 4 hours)**

Following the primary andexanet bolus and 120-minute infusion, the andexanet infusion will be continued at the low dose of andexanet (4 mg/min) if the surgery extends longer than the primary bolus and infusion. The extended infusion (1) must continue at least through the end of the surgery and (2) may additionally continue during the immediate post-operative period (per investigator discretion), and (3) should not exceed 4 hours.

Maximum Length of Dosing (Initial Bolus + 120 minute Infusion + Extended Infusion, < 6.5 hours):

The total duration of dosing including initial bolus, 120-minute infusion, and any extended infusion, should not exceed 6.5 hours. The limit of planned duration of infusion is stipulated to balance declining anti-fXa plasma levels and acceptable exposure to andexanet.

	
Criteria for Re-Dosing with Andexanet
 
Consider re-dosing with andexanet (low-dose bolus + 120 min infusion) only if:
 
 a) New, clinically significant, surgery-related post-operative bleeding occurs after initial course of andexanet (primary bolus + infusion and extended dosing, as applicable) is completed, AND b) The treating physician has clinical suspicion that the patient still has levels of FXa inhibition sufficient to contribute to the bleeding, AND c) Re-dosing initiation occurs within 12 hours after the completion of the surgical procedure.
Reference Therapy, Dose, and Mode of Administration	Not applicable.
Sample Size	Approximately 100 patients will be enrolled. After accounting for 20% attrition (e.g., canceled surgeries, discontinued and/or non-evaluable patients, or baseline anti-fXa activity analyzed by central laboratory less than the evaluability threshold), a sample size of 80 patients will provide an estimate of the proportion of patients achieving effective (excellent or good) hemostatic efficacy with a margin of error (half width of the 95% confidence interval [CI]) that is less than 11%.
Statistical Analysis Methods for Efficacy	
All efficacy analyses will be performed in the Efficacy Analysis Population. Unless otherwise specified, all CIs will be 2-sided and reported at the 95% confidence level.
 
The primary endpoint, the proportion of patients who have effective hemostasis, will be summarized with a 95% CI. The secondary endpoint, percent change in anti-fXa activity from baseline to the nadir for the evaluation period, will be assessed with a 2-sided 95% nonparametric CI for the median. For the exploratory endpoints, counts data will be summarized by observed rates and associated 95% CIs. Continuous endpoints will be summarized by means or medians and associated 95% CIs.

Statistical Analysis Methods for Safety	All safety analyses will be performed in the Safety Analysis Population. Safety will be assessed by examination of 30-day survival status, AEs (including SAEs and TEs), vital signs, physical examination, centrally adjudicated deaths, clinical laboratory measurements, and antibodies to andexanet, FX, FXa, and HCPs. These data will be descriptively summarized. All potential post-surgical major bleeding events and TEs will be confirmed by adjudication.

